*Natural history studies in Type 2 and Type 3 SMA (Vuillerot *et al.* 2013; Mercuri *et al.* 2016) have shown that patients 6–15 years of age have a greater likelihood of substantial worsening of their condition within 12–24 months of the observation period, which is likely related to growth and weight gain without an increase in muscle strength. Thus, the 6–15 years age group may be appropriate for demonstrating maintenance of motor function. A post hoc analysis conducted in this age group showed a statistically significant separation of 3.61 points ( $p=0.036$ ) on the MFM D1+D2 scores at 24 months.*

A responder analysis was performed by comparing the MFM score at Month 24 with the score at baseline. Patients were considered responders if their motor function score did not worsen at Month 24 compared to baseline. A similar approach was used for the HFMS by comparing the score at Month 21 with the score at baseline. For the MFM total score, olesoxime treatment for 24 months resulted in a higher responder rate (56.3%) compared to placebo (38.6%,  $p = 0.0419$ ). When the analyses were performed on the HFMS score, the relative risk was 1.82 [95% CI: 1.16; 2.86] in favor of olesoxime ( $p = 0.0091$ ), with 28.1% responders in the placebo arm, compared to 49.5% in the olesoxime arm. *The pre-specified analysis of electromyography (CMAP / MUNE), FVC,*

PedsQL, and CGI were inconclusive. However, a post hoc responder analysis of the CGI using a responder definition, which mirrors the stable or improved MFM/HFMS responder, showed a statistically significant effect favoring olesoxime (relative risk of 1.23 [CI: 1.01, 1.49];  $p=0.0361$ ). For the patient-/parent-reported CGI, a similar pattern was identified, with a trend favoring olesoxime (relative risk of 1.19 [CI: 0.99, 1.44];  $p=0.0640$ ).

SMA-related complications were reported as adverse events in a lower proportion of patients in the olesoxime group compared with placebo. Most importantly, a lower proportion of patients treated with olesoxime reported severe lower respiratory infections. All other adverse events were equally distributed in nature and severity: 63 (38.2%) patients experienced at least one serious adverse event, with a lower rate in the olesoxime arm compared with placebo (34 [31.5%] patients vs. 29 [50.9%] patients).

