4.1.4 Matched Patient Population

In order to account for differences between patients in the ITT population (treated) and those in the historical comparison population (untreated), several matching methods for

balancing baseline covariates will be considered depending on sample size, data availability and data quality.

If there is sufficient data, each individual in the ITT population will be matched to an individual in the historical comparison population (one-to-one matching) with respect to age, gender, SMA type and baseline MFM D1+D2 score. Gender and SMA type will be matched exactly, followed by optimal Mahalanobis distance matching within these groups for the age and baseline MFM D1+D2 score. In order to determine the 'closeness' between individuals to use in matching, we define the Mahalanobis distance, D_{ij} , between the i^{th} treated unit and j^{th} potential untreated unit:

$$D_{ij} = (x_i - x_j)^T \Sigma^{-1} (x_i - x_j)$$

where x_i and x_j are the observed values of the matching variables (age and baseline MFM D1+D2 score) for treated unit i and untreated unit j , respectively, and Σ is the variance covariance matrix of X in the untreated group. Optimal matching will be used to minimize the total distance $T = \sum D_{ij}$.

Patients in the ITT population who erroneously perform the MFM-20 assessment at the baseline visit will not be included in the matched patient population. MFM-20 assessments performed at any post-baseline visit will be set to missing.

If one-to-one matching does not produce enough matches (if > 10% of the ITT population is not matched), optimal full matching will be performed, where one untreated unit may be matched to more than one treated unit, but each treated unit will only be matched to one untreated unit. The maximum number of times each untreated unit is matched with a treated unit will be equal to the smallest integer value greater than or equal to the maximum ratio of treated to untreated units in each combination of gender and SMA type (Type 2 male, Type 2 female, Type 3 male and Type 3 female). The number of times each untreated unit is matched will be monitored to ensure that the treatment effect estimate is not based on only a small number of untreated units.

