4.4.1.2 Comparison with Natural History Data

Once the matched samples have been obtained, the covariate balance between the ITT and historical comparison populations, and between the treated and untreated groups in the matched patient population will be assessed (for age, gender, SMA type and baseline MFM D1+D2 score). Standardized mean differences and the ratio of the variances in the treated and untreated groups will be compared for each variable before and after matching. Medians, interquartile ranges (IQR) and ranges will also be compared for continuous variables.

If weights will be used in the analysis due to optimal full matching, they will also be used in calculating the balance measures. Each matched treated unit will receive a weight equal to one. Each matched untreated unit will receive a weight proportional to the number of treated units in its matched set divided by the number of untreated units in the set. For example, if a matched set contains one untreated unit and k treated units, the untreated unit would receive a weight proportional to $k/1=k$. The weights of the untreated units are scaled so that the sum of the weights is equal to the number of unique matched untreated units. Thus each matched untreated unit will receive a weight equal to $T_S/U_S / (T_N/U_N)$, where T_N and U_N are the total number of unique matched treated and untreated units, respectively, and T_S and U_S are the respective number of matched treated and untreated units in each matched set.

For a continuous variable the standardized mean difference, d , is defined as:

$$d = (x_t - x_u) / \sqrt{[(s_t^2 + s_u^2) / 2]}$$

where x_t and x_u denote the sample mean in the treated and untreated groups, respectively, and s_t^2 and s_u^2 denote the respective sample variances. For a binary variable the standardized mean difference is defined as:

$$d = (p_t - p_u) / \sqrt{[(p_t(1 - p_t) + p_u(1 - p_u)) / 2]}$$

where p_t and p_u denote the proportion of the binary variable in the treated and untreated groups, respectively (Austin 2009).

If the balance achieved between the two groups after matching is better than the covariate balance before matching, descriptive statistics for the MFM D1+D2 score will be presented for the matched patient population and the treatment effect will be estimated. An absolute standardized mean difference < 0.25 and a variance ratio of 0.5 to 2 for each variable indicate an acceptable balance between the two groups.

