Descriptive statistics for the actual values and change from baseline values in the MFM D1+D2 score will be presented. The results will be presented according to the timings of the MFM assessment visits in the ITT population: 26, 52, 78, 104 and every 26 weeks thereafter after baseline until the end of the study. As the MFM measurements in the natural history databases were not all collected at specific time points after baseline measurements, the measurements will be assigned to a scheduled study visit based on the time windows defined above. If more than one MFM measurement is recorded in the same time window the assessment closest to the target visit day will be used. Mean changes in the MFM D1+D2 score and corresponding 95% CIs over time will also be presented graphically.

Given sufficient data, the change from baseline in the MFM D1+D2 score at weeks 26, 52, 78 and 104 will also be analyzed using a mixed-effects model for repeated measures (MMRM). The model will include the treatment group, age, gender, SMA type, visit, treatment-by-visit interaction, and the baseline MFM D1+D2 score as covariates. Matched set will be included in the model as a random effect.

An unstructured variance-covariance matrix will be applied to model the within-patient errors. The restricted maximum likelihood method will be used for estimates of variance components. Denominator degrees of freedom will be estimated using the Kenward-Roger approximation. A treatment-by-time interaction contrast will be constructed to estimate the difference between the two groups in the mean change from baseline at each visit, and the 95% CI for the treatment difference will be reported.

If there are a sufficient number of patients in the historical comparison population for one-to-one matching to be performed, but the covariate balance between the treated and untreated groups after matching is worse than the balance before matching, then the optimal full matching described in Section 4.1.4 will be performed, and the covariate balance in this new population will be assessed. If the covariate balance between the treated and untreated groups after optimal full matching is worse than the balance before matching (and worse than the balance after one-to-one matching, if applicable), descriptive statistics for the MFM D1+D2 score will be presented for the historical comparison population, and the treatment effect in the pooled ITT and historical

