comparison populations will be estimated using the MMRM model described above, but without the matched set random effect.

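### The natural-history MMRM should let the effects of age and baseline MFM D1+D2 differ by visit, because one shared coefficient under-adjusts the Week 104 contrast (cheap improvement)

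*SAP*

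**What the plan says.** The secondary objective of effectiveness against natural history (Protocol 2.2) is estimated in SAP 4.4.1.2 by an MMRM on "the change from baseline in the MFM D1+D2 score at weeks 26, 52, 78 and 104". The fixed effects are listed in full: "The model will include the treatment group, age, gender, SMA type, visit, treatment-by-visit interaction, and the baseline MFM D1+D2 score as covariates". No other section adds a covariate-by-visit term. On the covariance, "An unstructured variance-covariance matrix will be applied to model the within-patient errors". SAP 4.4.2.1 applies the same comparison to the MFM total score.

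Before the model is fitted, treated and untreated patients are matched (SAP 4.1.4). "Gender and SMA type will be matched exactly", whereas age and baseline MFM D1+D2 are matched only by Mahalanobis distance. On balance, the SAP states: "An absolute standardized mean difference < 0.25 and a variance ratio of 0.5 to 2 for each variable indicate an acceptable balance". The condition for using the matched sample is weaker: "If the balance achieved between the two groups after matching is better than the covariate balance before matching". If full matching makes balance worse, the effect in the pooled ITT and historical "comparison populations will be estimated using the MMRM model described above, but without the matched set random effect".

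On the course of the disease, Protocol 3.3.1 reports that placebo progression was best described as linear, at -1.05 units/year. Protocol 1.2.2 cites natural history studies in which "patients 6–15 years of age have a greater likelihood of substantial worsening of their condition" over 12 to 24 months.

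**The concern.** A covariate that changes a linear rate of decline changes the score by an amount proportional to follow-up time. A single coefficient cannot follow that; it settles on a weighted average over the visits. Treatment-by-visit is free at every visit, so whatever part of an imbalance the shared coefficient leaves unadjusted goes straight into the reported treatment difference.

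Week 104 is the most exposed. It is the visit where a rate effect is largest, and it is the closest counterpart of the earlier trial's Month 24 endpoint. If treated patients are older than controls and older patients decline more slowly, olesoxime looks better than it is; if they are younger, it looks worse.

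Matching reduces the problem without removing it. Age and baseline MFM are not matched exactly, the 0.25 limit is a guide and not a condition, and balance is assessed on the matched set and not among patients still observed at Week 104. Some controls were followed for only 12 months (SAP 4.1.3.1) or 12 to 24 months (SAP 4.1.3.2). In the pooled fallback, covariate adjustment is the only protection.

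**Working it through.** The plan gives no bias, power or precision figure for this comparison, so there is none to reproduce. For scale, the earlier trial's result (2.0 points, 96% CI -0.25 to 4.25, Protocol 1.2.2) implies SE = 2.25/2.054 = 1.096. Then z = 2.0/1.096 = 1.83 and p = 0.068, in line with the printed 0.0676.

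**Formula.** Let t be 0.5, 1, 1.5 and 2 years, and let S be the 4x4 covariance of the changes. With complete data, the contrast at visit t equals the raw group difference minus beta x imbalance. Here beta = sum of w_t x b_t, with weights w = S^-1 1 / (1' S^-1 1). If the covariate acts on the rate, b_t = g x t. It follows that:

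- beta = g x t_eff, where t_eff = sum of w_t x t
- adjustment applied / adjustment needed = t_eff / t
- residual bias at t = imbalance x g x (t - t_eff)

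**Share of the needed adjustment that is applied** (covariance shapes assumed; the percentage is the random-slope share of Week 104 variance):

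| Covariance | t_eff (years) | Wk 26 | Wk 52 | Wk 78 | Wk 104 |
|---|---|---|---|---|---|
| Independence or compound symmetry | 1.25 | 2.50 | 1.25 | 0.83 | 0.62 |
| Random slopes 50% | 0.77 | 1.54 | 0.77 | 0.51 | 0.38 |
| Random slopes 75% | 0.43 | 0.87 | 0.43 | 0.29 | 0.22 |
| Random slopes 90% | 0.19 | 0.38 | 0.19 | 0.13 | 0.09 |

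Week 104 is under-adjusted in every row. Week 26 is over-adjusted only while t_eff exceeds 0.5 years, that is, up to a random-slope share of about 70%.

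**Size.** Assumed: age effect 0.08 to 0.12 points/year per year of age, and age SD 5.5 years. An age SMD of 0.25 is then 0.25 x 5.5 = 1.375 years.

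- Random slopes 50%: 1.375 x 0.08 x (2 - 0.77) = 0.14 and 1.375 x 0.12 x 1.23 = 0.20 points at Week 104. At Week 26, 1.375 x 0.08 x (0.5 - 0.77) = -0.03, and -0.04 with 0.12.
- Equal weights: 1.375 x 0.08 x 0.75 = 0.08, and 0.12 with 0.12.
- Random slopes 90%: 1.375 x 0.08 x 1.81 = 0.20, and 0.30 with 0.12.

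A separate simulation with no true effect (random-slope SD 1.5/year, error SD 2, 200 replicates) also gave 0.14 and 0.20 at SMD 0.25.

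**Effect of the interactions.** In a deliberately extreme simulation (SMD 1.0, g = 1 point/year per SD, 120 per group, 60 replicates, with and without missing control visits), the Week 104 bias was +0.97 to +1.86 as written. With covariate-by-visit terms it was -0.16 to +0.17, against a Monte Carlo SE of about 0.11 to 0.15. In the 200-replicate simulation the SD of the estimate was essentially unchanged (0.51 v 0.52).

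**The case against.** The best defence is that the realistic error is small. After matching to an age SMD of 0.25 it is 0.14 to 0.20 points, or 0.13 to 0.18 of the earlier trial's standard error of 1.096. The comparison is estimation only, and the primary objective is safety. That stands, and it limits the priority of the point.

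The age slope is also assumed. Protocol 1.2.2 says only that one age band is likelier to worsen substantially, which is not a linear gradient; the linear rate in Protocol 3.3.1 describes the placebo mean. Neither document says that baseline MFM or SMA type changes the rate. So the size cannot be fixed from the documents, and a linear age-by-visit term may itself fit imperfectly. It would still be less restrictive than a constant effect.

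Other analyses touch the subject: a continuous-time disease-progression model (Protocol 6.12), optional covariate modelling (Protocol 6.7) and graphs by age group (SAP 4.4.5). None of them changes the MMRM contrast.

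A reader might infer four stronger things:

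- **Week 26 is always over-adjusted.** It is not. The sign reverses when random slopes dominate the variance.
- **Imbalance in any covariate matters.** Gender and SMA type are matched exactly, so in the matched analysis the point concerns age and baseline MFM. SMA type comes in with the pooled fallback.
- **The fallback brings a large bias.** A 4-year age gap there gives 0.41 to 0.65 points under the same assumed slopes. But the fallback runs only if full matching worsens balance. In a simulation of the matching rule (assumed 130 treated, 60 to 200 controls, age SD 6), a 4-year gap never led to worse age balance in 600 runs. The age SMD fell from about 0.7 to 0.33-0.40. That still exceeds 0.25, so the matched-sample point survives.
- **The common covariance matrix makes the interval too narrow.** Two-sample arithmetic gives 91% coverage with 130 treated, 60 controls and SDs of 4 and 6. It gives 95% with equal groups and 98% with the SDs reversed. The documents supply neither the SDs nor the control numbers.

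**Conclusion.** The point holds as a cheap improvement. If age or baseline MFM acts on the rate of decline, the model in SAP 4.4.1.2 under-adjusts Week 104 under every covariance tried, and the remainder biases the treatment contrast in the direction of the imbalance. The documents support this for age; for baseline MFM it is plausible but not stated.

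The size rests on the assumed slope of 0.08 to 0.12 points/year per year of age. It is about 0.14 to 0.20 points at an age SMD of 0.25 (0.08 to 0.30 across the covariance shapes above), or 7 to 10% of the earlier trial's 2.0 points. It scales with the imbalance: at SMD 0.33 to 0.40 it would be about 0.18 to 0.32 points. Which group will be older is unknown, since the control age window in SAP 4.1.3 can extend beyond the treated range at both ends. The documents do not show that the comparison is biased towards olesoxime, or that its interval is wrong.

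**What to change.** In SAP 4.4.1.2, add age-by-visit and baseline-MFM-by-visit interactions to the MMRM, for the D1+D2 score and for the total score, in both the matched analysis and the pooled fallback. In the pooled fallback, also add SMA-type-by-visit. A version using the SAP 4.4.5 age split (6-15, 16 and over) by visit would check the linear age term.

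With four visits, each interaction costs three fixed-effect parameters: six in the matched model, and nine in the fallback with SMA type as Type 2 against Type 3. The single Type 1 patient and the one control chosen for that patient cannot support a type-by-visit term, so the SAP should say how they are handled there. The downside is that late control visits may be sparse and the Week 104 coefficients imprecise; the SAP should state which interaction is dropped first if the model does not converge. Group-specific covariance matrices can be offered as a sensitivity analysis, but the documents give no ground for making them the main model.

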*Attempts to increase the systemic exposure of olesoxime by increasing the daily dose from 10 mg/kg QD to 20 mg/kg QD (using a solution formulation) produced a marginal (~20%) increase in  $AUC_{0-\infty}$ . The limited increase in bioavailability is thought to be due to saturable absorption of olesoxime. However, when the 20 mg/kg dose was divided into two doses, 10 mg/kg each, administered approximately 12 hours apart, an increase in the  $AUC_{0-\infty}$  of 100% was observed, while  $C_{max}$  was only increased by ~20%. The preliminary results of the study also indicated that a dose of 30 mg/kg of olesoxime in suspension formulation divided into two doses (15 mg/kg each) resulted in an increase of ~120% in AUC and ~56% increase in  $C_{max}$ , compared with a single dose of 10 mg/kg as suspension. Therefore, although a dose of 10 mg/kg BID in suspension form was not tested in Study BP39378, this dose is projected to produce a ~100% increase in AUC and the average steady-state plasma concentration of olesoxime, while  $C_{max}$  should only increase by 20% to 30%. The increase in exposure is assumed to lead to a clinically meaningful increase in motor function for patients (2-point increase in the MFM D1 + D2 efficacy score) as detailed before.*

*The total daily dose in this study will not exceed 2000 mg. Thus, for patients with body weight >100 kg, the administered dose will be 1000 mg BID. The maximum dose of 2 g/day forms the basis of the technical IMP specifications in the drug manufacturing process and cannot be exceeded for this reason.*

*The drug will be provided as liquid suspension formulation of olesoxime (100 mg/mL) for oral administration or via gastrostomy tube. Due to the weight-based dosing, it is required that body weight be measured and recorded at every study visit. The study drug should be administered BID orally or via a naso-gastric or gastrostomy tube with breakfast and dinner, preferably at the same time of the day throughout the study.*

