#### **4.4.12 Clinical Global Impression of Change**

*The CGI-C is a single-item measure of change in global health that uses seven response options: Very Much Improved, Much Improved, Minimally Improved, No Change, Minimally Worse, Much Worse, and Very Much Worse. It is a widely used endpoint in clinical trials across a variety of disease areas. Clinicians will score patients using this scale based on their impression of change in the patient's global health since baseline. To enhance inter-rater consistency, an instructions document (developed with input from clinical experts) will be provided, which includes examples for each of the response options.*

*The same clinician should complete the CGI-C at all specified visits for an individual patient. The CGI-C will be administered at the dose increase visit and study Visits 5, 6, and 7.*

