## **6.7           SECONDARY ANALYSES**

The change from baseline in MFM D1+D2 and MFM Total Score will be summarized at each visit using descriptive statistics. *The data will be summarized by the dose being taken at the time of the assessment.* Mean changes and 95% confidence intervals over time will be presented graphically. Summary statistics by age and SMA type will also be provided.

Where available, similar descriptive statistics may be presented for the Natural History Data.

Statistical modelling approaches may be used to explore the effects of differences in baseline covariates. Details will be provided in the SAP.

The incidence of disease associated medical complications and procedures will be summarized. *The data will be summarized by the dose being taken at the onset date of the event.*

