3. STUDY CONDUCT

3.1 RANDOMIZATION

BN29854 is a single arm, open-label study, and all patients receive olesoxime at 10mg/kg q.d.

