4.4.1.1 Handling of Missing Data

- All observed assessments will be included in the analyses. No imputation for missing MFM scores will be performed.
- Following the death of a patient, MFM scores will be set to missing.
- If an individual MFM item is missing or was 'Not done,' the item will be set to zero in accordance with the MFM user manual.

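### The SAP's natural-history MMRM has no dose term and no rule for scores after the dose increase, so its later-visit contrasts can mix QD and BID

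*SAP*

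**What the plan says.** **SAP.** Section 4.4.1.2 plans that "the change from baseline in the MFM D1+D2 score at weeks 26, 52, 78 and 104 will also be analyzed" by MMRM, given sufficient data. On the terms: "The model will include the treatment group, age, gender, SMA type, visit, treatment-by-visit interaction, and the baseline MFM D1+D2 score as covariates". Matched set is a random effect. The treatment factor has two levels, treated and untreated, and the contrast is built to "estimate the difference between the two groups in the mean change from baseline at each visit". If matching does not improve balance, the fallback model on the pooled populations drops only the matched-set effect. Section 4.4.2.1 applies the same comparison to the MFM total score.

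On which scores enter, Section 4.4.1.1 says: "All observed assessments will be included in the analyses. No imputation for missing MFM scores will be performed". Nothing is set aside at a change of dose. Sections 2 and 3.1 describe a single regimen: "all patients receive olesoxime at 10mg/kg q.d". The descriptive MFM tables are split by treatment in the earlier trial, not by current dose. The SAP mentions protocol version 3 when it explains the removal of the HFMS. It does not mention Version 4.

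**Protocol Version 4.** The study began at 10 mg/kg QD. Consenting patients move to 10 mg/kg BID and the rest stay on QD (1.3, 3.1.1.3, 3.1.1.4), so both doses can occur at one visit. For MFM, Section 6.7 says: "The data will be summarized by the dose being taken at the time of the assessment". That rule is written for descriptive summaries, and the same section leaves modelling details to the SAP. Section 3.3.1 gives the gain assumed from the higher exposure: a "2-point increase in the MFM D1 + D2 efficacy score".

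**The concern.** The protocol separates the doses in its descriptive MFM tables, but neither document carries that separation into the model-based comparison with natural history. Wherever both doses occur at a visit, the model returns one treated-minus-untreated difference that averages over them, in proportions nobody has fixed.

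The sponsor raised the dose because it expects a larger effect, so the average is not neutral. If the BID share grows from visit to visit, the contrasts rise for that reason alone. A reader who relies on the SAP's description of the treatment would take the rise as the course of the effect under QD. The contrast bears directly on the secondary objective of effectiveness against natural history (Protocol 2.2).

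**Working it through.** **Inputs**
- Projected BID-minus-QD difference, d: 2 points (Protocol 3.3.1).
- Exposure-response slope: 0.281 points per mg/L, relative standard error 36% (Protocol 3.3.1).
- Average trough concentration on QD: Protocol 1.2.2 equates 801 ng/mL with 9.5% of it, so 801 / 0.095 = 8,432 ng/mL, or about 8.43 mg/L.
- Scale: the earlier trial's QD effect was 2.0 points at Month 24, 96% CI -0.25 to 4.25 (Protocol 1.2.2). Modelled placebo decline was 1.05 points per year (Protocol 3.3.1).
- BID share of treated scores at a visit, f: not in the documents, so the full range is shown.

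**1. Does the sponsor's 2 points fit its own figures?** Doubling exposure adds about 8.43 mg/L, and 0.281 × 8.43 = 2.37 points. The standard error of the slope is 0.281 × 0.36 = 0.101, so its approximate 95% range is 0.281 ± 1.96 × 0.101 = 0.083 to 0.479. Multiplied by the added concentration, that is 0.70 to 4.04 points. The stated 2 points is in line with this, but imprecise.

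**2. What does a mixed contrast estimate?** With QD effect q at a visit and BID effect q + d, the pooled contrast is (1 - f)q + f(q + d) = q + fd. With d = 2:

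| f | Above QD effect (2f) | Below BID effect (2(1 - f)) |
|---|---|---|
| 0 | 0 | 2.0 |
| 25% | 0.5 | 1.5 |
| 50% | 1.0 | 1.0 |
| 75% | 1.5 | 0.5 |
| 100% | 2.0 | 0 |

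This lets the whole gain appear at once after the switch. A slower onset makes the shift smaller, so for a 2-point gain these are upper values.

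**3. Which visits are affected?** The effective date of Version 4 is not given, but its text cites information as of September 2017 (Protocol 1.2). It also reports a 12-month analysis of this study already made at the earlier dose (1.2.4). I assumed baselines from March to November 2016 and BID available from some date between October 2017 and April 2018. The earliest patients are then at about Weeks 83 to 109 when BID becomes possible, and the latest at about Weeks 45 to 71. On that calendar Week 26 is all QD, Week 52 all or nearly all QD, and Weeks 78 and 104 mixed. Under a stretched case (baseline end of March 2017, BID from October 2017), a patient reaches BID at about Week 26, so some Week 52 scores could be on BID.

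**4. Does the model behave as step 2 predicts?** A simplified simulation used one treated group with treatment-by-visit terms, 300 runs, 120 patients per group, an assumed SD of 4 and within-patient correlation of 0.6. It omitted the baseline covariates and matched sets.

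| Week | Assumed f | QD truth | BID truth | Mean MMRM contrast |
|---|---|---|---|---|
| 26 | 0 | 0.25 | 2.25 | 0.29 |
| 52 | 0 | 0.50 | 2.50 | 0.51 |
| 78 | 25% | 0.75 | 2.75 | 1.30 |
| 104 | 75% | 1.00 | 3.00 | 2.53 |

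Step 2 predicts 0.75 + 0.5 = 1.25 at Week 78 and 1.00 + 1.5 = 2.50 at Week 104. The early contrasts stay at the QD value, and the late ones fall between the doses.

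**The case against.** **Visit-specific contrasts.** A reader might infer that the whole analysis belongs to neither dose. The documents do not support that: the model gives a separate contrast at each visit, and a contrast built on QD scores remains a QD estimate. This stands, and it confines the problem to the later visits.

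**Other comparisons exist.** A reader might also call this the only comparative efficacy estimate. It is not. The MFM total score has its own natural-history comparison, and complication rates are set beside the NatHis-SMA study (SAP 4.4.2.4). Exposure-response and disease-progression work is reported separately (Protocol 6.9, 6.12). But the total score uses the same model, the SAP does not split the complication rates by dose, and the separate modelling is not described as a contrast with natural history by dose.

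**Weak evidence for Week 52.** The protocol says "The CGI-C will be administered at the dose increase visit and study Visits 5, 6, and 7", and Visits 5 to 7 are Weeks 52 to 104. That might suggest BID scores at all three, but a scheduled assessment does not show the dose in use. The increase may be made at a regular visit, with BID starting only the day after the Holter monitor is removed (Protocol 3.1.1.4), so that visit's MFM score may still be on QD.

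**No stated intention to mislabel.** One might infer that the results would be presented as a QD effect. The SAP labels the contrast treated versus untreated. A SAP that was not updated to Version 4 explains the text better than a decision to pool.

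**The all-scores contrast is a legitimate target.** The objective names olesoxime without a dose, the study is described as an effectiveness study, and the protocol title is now BID. This stands. It argues for labelling that contrast properly and against replacing it with a QD-only analysis.

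**Limited weight.** No hypothesis is tested, the MMRM depends on sufficient data, and f and d are uncertain. This also stands. It lowers the stakes without supplying the missing rule.

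**Conclusion.** The concern holds for the later visits. Followed as written, the natural-history MMRM can mix QD and BID scores at Weeks 78 and 104, and possibly in part of Week 52, with nothing in either document to separate or label them. Week 26, and most or all of Week 52, are plausibly QD estimates.

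On the sponsor's 2-point projection the shift from the QD effect is at most 2f points. At f = 50% that is 1.0 point, half of the earlier trial's estimated effect and close to one year of modelled placebo decline. The size rests on that projection, on immediate onset, and on an f that the documents do not give. The choice of visits rests on assumed calendar dates. The absence of a dose term and of a post-increase rule rests on the text alone. As the study is descriptive, what is at risk is the interpretation of the late contrasts, not an error rate.

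**What to change.** 1. Align the treatment description in SAP 2 and 3.1 with Protocol Version 4.
2. In SAP 4.4.1.2, report the MMRM twice. Run A uses all scores and is labelled as the QD-then-BID regimen versus natural history, with a note that patients who declined the increase stayed on QD. Run B sets treated scores after the first BID dose to missing and is labelled QD versus natural history. Classify each score by the date of the first BID dose, not by visit.
3. State which run is primary.
4. Show the number of QD and BID scores at each visit beside both sets of contrasts.
5. Do the same for the MFM total score (SAP 4.4.2.1) and in the fallback pooled model.

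**Cost.** SAP wording and one extra model run per endpoint, with no new data collection. Run B has fewer treated scores and wider intervals at the late visits. It also assumes that the removed scores are missing at random. Timing follows the amendment in part, but consent is voluntary, a patient may reconsider later, and medical condition can delay the switch (Protocol 3.1.1.4, 4.4.1.1). Late QD scores may thus come from a selected group, and the SAP should say so. Neither run estimates BID alone, because BID scores follow earlier QD exposure.
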